160 **SECTION B: RESEARCH METHODOLOGY**

161

162 **B1. ABSTRACT**

163
164 Endurance exercise elicits skeletal muscle and systemic inflammation, reflected in large part by
165 increases in circulating concentrations of the pleiotropic cytokine, interleukin-6 (IL-6). Circulating
166 IL-6 facilitates skeletal muscle tissue repair and serves as an energy sensor during prolonged
167 endurance exercise by upregulating glycogenolysis to maintain blood glucose. The IL-6
168 response to endurance exercise is normally attenuated with adequate rest and recovery as
169 skeletal muscle adapts with training. However, performing repeated bouts of prolonged and
170 unaccustomed, muscle damaging (i.e., eccentric loading) endurance exercise may be
171 detrimental to performance and limit the adaptive responses to exercise by diminishing the
172 absorption of key nutrients (i.e., iron). Warfighters are commonly exposed to such exercise
173 bouts during sustained training and combat operations (SUSOPS), the effects of which may be
174 exacerbated by negative energy balance. We recently reported that IL-6 and hepcidin, a
175 hepatic-derived protein that arises in response to inflammation and limits iron absorption,
176 increased by approximately 245% and 33%, respectively in Norwegian Soldiers participating in
177 a short-term (96 h) Arctic SUSOPS [1]. Circulating hepcidin concentrations post-SUSOPS were
178 associated with total daily energy expenditure ($r = 0.4$), energy intake ($r = -0.26$), and energy
179 balance ($r = -0.43$), suggesting that nutritional interventions designed to increase energy intake
180 during SUSOPS may attenuate IL-6 and its untoward downstream effects by limiting the

181 magnitude of energy deficit. However, these data, which were derived from an uncontrolled
182 military field study, are not indicative of causality and changes in iron absorption. Therefore, to
183 define the putative role of energy balance on IL-6 and its downstream effects, we will conduct a
184 controlled laboratory study that simulates the physiological stressors imposed during SUSOPS
185 to determine if the IL-6 response is exacerbated by underfeeding. Fifteen male, weight-stable,
186 active duty military personnel (aged 18 – 39 years) will be recruited to participate in a 22 d,
187 longitudinal study. The study is comprised of four sequential phases: 1) a 72 h SUSOPS, 2) a 7
188 day recovery period (Recovery 1), 3) a second, 72 h SUSOPS, and 4) a final, 7 d recovery

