268 response to exercise include mode and location of muscle mass, frequency, duration, intensity,
269 and training status [reviewed in [5, 13, 17, 18]]. In general, eccentric and strenuous exercise
270 involving multiple muscle groups for prolonged durations produces the greatest increase in IL-6
271 as a cytokine and myokine, respectively. Although skeletal muscle damage is not required for
272 the release of IL-6 from muscle during and immediately following exercise [5], it is important to
273 note that the release of muscle- and immune cell-derived IL-6 is not mutually exclusive. Higher
274 concentrations of muscle-derived IL-6 during and immediately following exercise generally
275 indicate greater muscle damage, leading to an increase in immune cell infiltration and the time
276 required for tissue repair and regeneration.

277 **Potential Detriments of Inflammation on Iron Absorption during Sustained Operations**

278 The release of IL-6 during exercise has been described as a double-edged sword [20], as IL-6
279 has the potential for both beneficial and detrimental effects. Beneficial adaptations resulting
280 from exercise occur when the stressor dose and the exercise bout are within a specific range
281 and followed by a rest period [21], whereas detrimental effects may occur when the dose or
282 exercise bout is excessive and not followed by periods of adequate rest and nutrition. For
283 example, repeated bouts of exercise on the same day or over the course of two days elevates
284 circulating concentrations of immune cells and induces a more pronounced increase in plasma
285 IL-6 as compared to a single bout of exercise [22, 23]. Further, repeated bouts of exercise
286 without adequate rest and nutrition may result in decreased performance, particularly if muscle
287 glycogen concentrations are low prior to exercise (e.g., fasted state, inadequate recovery, etc.)
288 or if the duration of exercise is too long to maintain glycogen stores.

289 Importantly, sustained elevations in IL-6 may result in a decline in nutrient absorption,
290 particularly the nutritionally essential mineral iron. Circulating levels of iron increase immediately
291 following exercise and decline with recovery [24]. Inflammation, specifically the release of IL-6,
292 is known to contribute to the decline in iron (termed the 'hypoferremia of inflammation'). For
293 example, infusion of humans or animals with IL-6 reduces circulating concentrations of iron

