518 dynamics and biological pathways within the human host that are affected by
519 military-relevant stress and are associated with physical and cognitive performance,
520 and identify novel markers of physiological stress.

521

522 **B5. RESEARCH PLAN**

523

524 **B5.1 Research Design**

525

526 This randomized cross-over study will consist of four sequential phases (SUSOPS 1, Recovery
527 1, SUSOPS 2, and Recovery 2).

528

529 **B5.2 Research Subjects/Population(s)**

530

531 **B5.2.1 Subject Population(s)**

532

533 Healthy, recreationally-active adult men, who are active duty military, will be recruited to
534 participate in this study. Male subjects were chosen because of known sex differences in
535 iron status and absorption and differences in their response to exercise, including the IL-
536 6 response to exercise [62, 63]. Pending the outcomes from this study, future, more
537 targeted studies will be designed to address potential sex-based differences in
538 physiological responses to SUSOPS.

539

540 **B5.2.2 Number of Subjects, Records, and/or Specimens**

541

542 This protocol requires 15 subjects complete testing to provide 80% power to detect
543 significant differences in circulating hepcidin responses between SUSOPS 1 and
544 SUSOPS 2. Up to 60 subjects will be enrolled to account for attrition and screening

545 failures in order to get complete data on 15 subjects. See section B5.8.1 for details on
546 sample size calculations.
547

548 **B5.2.3 Inclusion Criteria**

- 549 • Men who are active duty military, aged 18 – 39 years
- 550 • Weight stable in the past 2 months (\pm 2.27 kg)
- 551 • Healthy without evidence of chronic illness, medication use, or musculoskeletal injury
- 552 as determined by the USARIEM Office of Medical Support and Oversight (OMSO)
- 553 • Recreationally active (2-4 days per week aerobic and/or resistance exercise)
- 554 • Refrain from taking any pain-relievers (e.g., acetaminophen), nonsteroidal anti-
- 555 inflammatory drugs (e.g., aspirin, Advil®, Aleve®, Naprosyn®), or any other aspirin-
- 556 containing product for 10 days before starting and at least 5 days after completing
- 557 the study
- 558 • Refrain from the use of alcohol and nicotine for the duration of the study
- 559 • Willing to refrain from alcohol, smoking any nicotine product (includes e-cigarettes),
- 560 vaping, chewing tobacco, caffeine, and dietary supplement use, and from

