831 $\dot{V}O_{2peak}$. Volunteers will begin with a 5 min warm-up at 50% $\dot{V}O_{2peak}$ before beginning the
832 protocol. After a warm-up period, the cycle ergometer protocol is comprised of repeated periods
833 of 2 min of work at $80 \pm 5\% \dot{V}O_{2peak}$ followed by 2 min of recovery at $50 \pm 5\% \dot{V}O_{2peak}$. The
834 protocol will last approximately 50-min (12 work:rest cycles). To ensure familiarity with the
835 testing procedures, volunteers will perform one practice session during the baseline pre-study
836 period. Volunteers will be permitted to consume water *ad libitum* during the protocol.

837

838 After completing the glycogen depletion protocol, volunteers will be fed a controlled diet
839 prescribed to maintain energy balance and provide at least 6.0 g carbohydrate $\cdot kg^{-1} \cdot d^{-1}$ (~55-
840 60% of total energy consumed) to ensure adequate glycogen repletion and homogeneous
841 glycogen levels within and across volunteers between SUSOPS phases (BAL and NEG BAL).
842 All food and beverages (except water) will be prepared and provided by study dietitians and
843 consist largely of military combat ration and supplemental food items.

844

845 **Determination of Fractional Iron Absorption**

846 Volunteers will undergo three acute fractional iron absorption studies (Iron Studies 1, 2, and 3).
847 The studies will occur on days 2, 6, and 16 in the morning (~0000 h) after an 8 h fast. The iron
848 studies on days 6 and 16 will occur ~3 h after completing the last exercise bout of the SUSOPS
849 to correspond to peak hepcidin responses to exercise. An indwelling 18 gauge intravenous
850 catheter will be placed in the antecubital fossa (or distally) and a baseline blood sample will be
851 drawn before consuming the iron isotope (0 min). Volunteers will then consume a 300 mL drink
852 containing 3.8 mg iron (representative of dietary iron in an iron-rich meal) as isotopically labeled
853 $^{54}FeSO_4$, $^{57}FeSO_4$, or $^{58}FeSO_4$ (Trace Sciences International). Venous blood samples will be
854 collected at 20, 40, 60, 120, 240, and 360 min-post iron loading [70] to assess the effects of a
855 transient exercise-induced increase in IL-6 (and hepcidin) on the appearance of absorbed iron
856 in blood.

857

858 **Percutaneous Muscle Biopsy of the Vastus Lateralis**

859 Percutaneous muscle biopsies will be obtained from the vastus lateralis using a 5 mm

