We have previously shown that an increase of intestinal permeability of 55-60% is associated with inflammation in military-relevant environments (USARIEM protocol 14-33HC [44]). Using means (pre-SUSOPS sucralose excretion = 2.0%), standard deviations (SD = 1.1), and correlations for repeated measurements of sucralose excretion (r = 0.5) from 14-33HC, we estimate that 14 subjects will allow detection of a main effect of study phase (BL vs. SUSOPS-NEG BAL vs. SUSOPS-BAL) if the effect size of SUSOPS-BAL vs. SUSOPS-NEG BAL on intestinal permeability is medium (~20% decrease) at power = 0.80 and alpha = 0.017 (<https://glimmpse.samplesizeshop.org/>). Of note, larger effect sizes have been reported in studies investigating the effects of nutritional interventions on intestinal permeability during exercise [105]. Additionally, we feel that it is likely that the SDs measured in this laboratory study will be slightly lower than those measured in our previous study (14-33HC) which was conducted in a field environment. A 25% decrease in the SD would allow us to detect a main effect of phase with 11 subjects at power = 0.80 and alpha = 0.017. As such we expect an n of 11 to 15 will provide adequate power to detect a main effect of phase on intestinal permeability.

Power calculations for appetite-mediating hormones outcomes were conducted using data obtained during USARIEM protocol H10-09 [73, 106]. In that study an energy deficit (3700 kcal/d) slightly greater than that which will be imposed in this study resulted in a 2.5-fold decrease in fasted acyl ghrelin, a 2.2 fold decrease in leptin, a 1.7-fold decrease in PYY, and a 3-fold increase in PP concentrations concomitant to an ~11-fold increase in appetite and overeating during recovery from energy deficit. Based on these results we expect to observe the hormone responses in the table below where fasting concentrations will be approximately maintained during BAL, and the maximal difference between BAL and NEG BAL will be observed on SUSOPS day 3 followed by a full recovery of hormone concentrations by recovery day 3. For all but PP, 12 subjects will provide ≥80% power at alpha = 0.01 to detect a phase-by-time interaction.

	BAL				NEG BAL				SD	r	n
	S-d1	S-d3	R-d1	R-d3	S-d1	S-d3	R-d1	R-d3			
Ghrelin	185	185	185	185	185	75	135	185	90	P,0.65; T, 0.60	11
Leptin	9	9	9	9	9	4.1	6.5	9	5	P,0.60; T, 0.75	11
PYY	170	170	170	170	170	100	135	170	170	P,0.85; T, 0.85	12
PP	65	65	65	65	65	195	130	65	100	P,0.30; T, 0.30	19

1425

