1455 liberal false discovery rate (e.g., 0.20) may be used to reduce type 2 error rates and
1456 increase power. For microbiome analysis, shotgun sequencing (maximum 50 million
1457 pair end reads) of 15 participants will achieve $\geq 69\%$ power to detect a true difference in
1458 relative abundance of at least 1.5 fold with group coefficient variation 1.3, and false
1459 discovery rate of 0.05. Again, a more liberal false discovery rate (e.g., 0.20) may be
1460 used to reduce type 2 error rates and increase power. Power calculations were
1461 conducted using pairwise distances and PERMANOVA power with respect to effect size.
1462 However, power will be enhanced by correlating the blood mRNA data with other omics
1463 readouts derived from saliva (microRNA-seq, metabolomics and microbiome) and blood
1464 (targeted microRNA and metabolomics), and by temporal sample collection. As such,
1465 we expect that 15 participants will provide adequate power to detect differences in blood
1466 mRNA expression, and gut microbiome community and genome composition between
1467 study phases, and correlations between these parameters and other –omics readouts.

1468 **B5.8.2 Data analysis**

1469
1470
1471 Statistical analyses will be conducted using either SPSS (IBM Corp. Armonk, NY), SAS
1472 9.3 (SAS Institute Inc., Cary, NC), or equivalent. Common descriptive statistics will be
1473 used to describe volunteer characteristics. Shapiro-Wilk tests will be used to determine
1474 normality of data, and transformations will be applied as appropriate to ensure model
1475 assumptions are met. Correlation and multiple regression will be used to evaluate
1476 relationships between study outcomes.

1477 **Primary Objectives**

1478
1479 Linear mixed models will be used to determine main effects of phase (SUSOPS BAL and
1480 SUSOPS NEG BAL), time within phase, and their interaction on inflammation, iron
1481 absorption, mood/cognitive, and measures of muscle, nutritional, and metabolic
1482 homeostasis. If phase by time interactions are observed, a Bonferroni correction will be
1483 applied for multiple comparisons. Statistical significance will be set at $P < 0.05$. To test
1484 for carryover effects a main effect of group (SUSOPS BAL first, SUSOPS NEG BAL first)

1485 and a group-by-phase interaction will be included in initial models. These terms will be
1486 removed if they do not significantly contribute to the overall fit of the model. When

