1487 significant phase-by-time interactions are observed post hoc comparisons will be made
1488 using paired t-tests with Bonferroni corrections.

1489

1490 **Secondary Objectives**

1491 Linear mixed models will be used to examine changes in intestinal permeability and
1492 gastrointestinal transit time. Models will include subject as a random factor, and study
1493 phase as a fixed factor. To test for carryover effects a main effect of group (SUSOPS
1494 BAL first, SUSOPS NEG BAL first) and a group-by-phase interaction will be included in
1495 initial models. These terms will be removed if they do not significantly contribute to the
1496 overall fit of the model. When a significant main effect is observed post hoc
1497 comparisons will be made using paired t-tests with Bonferroni corrections.

1498

1499 Fecal metabolomics data will be visualized using hierarchical average-linkage clustering
1500 and principal components analysis. Bacterial taxonomic data will be visualized using
1501 hierarchical average-linkage clustering and principal coordinates analysis of beta (i.e.,
1502 between samples) diversity scores (e.g., Bray-Curtis, and weighted and unweighted
1503 UniFrac). Alpha (i.e., within-sample) diversity will be calculated for taxonomic data using
1504 Shannon, Simpson and Chao1 indices. Linear mixed models will be used to examine
1505 changes in biomarkers of gut health, fecal metabolite concentrations, and alpha diversity
1506 over time. Models will include subject as a random factor, and study phase, time within
1507 phase, and their interaction as fixed factors. To test for carryover effects a main effect of
1508 group (SUSOPS BAL first, SUSOPS NEG BAL first) and a group-by-phase interaction
1509 will be included in initial models. These terms will be removed if they do not significantly
1510 contribute to the overall fit of the model. Models for bacterial taxa and gene abundance
1511 will be analyzed using the R statistical software package “DESeq2” or equivalent. The
1512 Benjamini-Hochberg correction will be used to control the false discovery rate in
1513 microbiome-specific and metabolite models. Data analysis will be completed using
1514 SPSS, XLSTAT, R, Qiime, or similar software as needed.

1515

1516 Linear mixed models will be used to examine changes in appetite-mediating hormone
1517 concentrations, appetite ratings, food preferences, food choice during recovery (i.e., diet

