1518 macronutrient proportion and energy intake). Models will include subject as a random
1519 factor, and study phase, time within phase, and their interaction as fixed factors.
1520 Separate analysis will be conducted for fasted and post-exercise appetite-mediating
1521 hormones. To test for carryover effects a main effect of group (SUSOPS BAL first,
1522 SUSOPS NEG BAL first) and a group-by-phase interaction will be included in initial
1523 models. These terms will be removed if they do not significantly contribute to the overall
1524 fit of the model. When significant phase-by-time interactions are observed post hoc
1525 comparisons will be made using paired t-tests with Bonferroni corrections.

1526

1527 The mRNA seq strand-specific libraries will be assayed using the Illumina HiSeq
1528 platform. Paired end reads of the strand-specific RNA sequences (RNA-Seq) will be
1529 generated using NextSQ from one flow cell with eight lanes, producing at least 30 million
1530 reads of 100 bases per sample. Based calling and expression analysis will be conducted
1531 using the Illumina-provided tool CASAVA. miRNA (20-40 bp) will be size selected from
1532 total RNA and will be processed by Illumina NextSQ. Image analysis and base calling
1533 will be performed using the newest available version of the Illumina pipeline.

1534 Preprocessing of raw base calls and sample de-multiplexing will be performed using the

1535 standard open source tool CASAVA. The microRNA read count matrix will be generated
1536 by a series of tool kits of latest version including CutAdapt, short read aligner Bowtie and
1537 PICARD. Metabolomics and proteomics reads will be processed by the software offered
1538 by the vendors namely Waters Corporation and BioRad, respectively.
1539

1540 Using a systems approach, we will integrate multiple levels of biological information. We
1541 have published the analysis pipeline and implemented it successfully in the past. Our
1542 pipeline uses industry standards and our established SOPs. We will start by analyzing
1543 and processing data at the analyte level for each data type such as mRNA expression,
1544 miRNA expression, microbiome, proteomics, and metabolomics. We will first examine
1545 the confounding factors or batch effects caused by non-biological factors, such as the
1546 technical error, sample processing date etc., using principal component analysis and

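### The term the plan tests as carryover is the period effect; it can be deleted on a significance test, and the post hoc paired t-tests ignore it

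*Combined protocol and SAP*

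**What the plan says.** B5.1 sets out the design: "This randomized cross-over study will consist of four sequential phases (SUSOPS 1, Recovery" 1, SUSOPS 2 and Recovery 2). In that sentence a phase is a stretch of calendar time. In B5.8.2, Primary Objectives, phase is instead the diet condition (BAL or NEG BAL), and group is which diet came first.

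To test for carryover, the primary models add a group main effect "and a group-by-phase interaction will be included in initial models. These terms will be" removed unless they add significantly to model fit. The rule recurs in three secondary model sets:
- permeability and transit time;
- gut-health markers, fecal metabolites and alpha diversity;
- appetite, food preference and food choice, where it reads "models. These terms will be removed if they do not significantly contribute to the overall" fit.

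No term for SUSOPS 1 versus SUSOPS 2 is specified under that name.

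Post hoc comparisons for the primary, permeability/transit and appetite outcomes are made "using paired t-tests with Bonferroni corrections".

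Two measurement schedules matter. For fractional iron absorption (B5.3), "The studies will occur on days 2, 6, and 16 in the morning", with 57Fe given on day 6 and 58Fe on day 16. Permeability is sized in B5.8.1 for a "main effect of study phase (BL vs. SUSOPS-NEG BAL vs. SUSOPS-BAL"), and its model in B5.8.2 has phase but no time term.

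**The concern.** Diet crossed with diet order identifies which SUSOPS a measurement came from. The group-by-phase term is therefore the period contrast. Of the two terms labelled carryover, only the group main effect is the conventional carryover term. The plan thus makes the period adjustment conditional on a low-powered test, and the paired t-test has no place for it at all.

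A period effect is plausible on the protocol's own account, although its direction is unsettled. The abstract says the IL-6 "response to endurance exercise is normally attenuated with adequate rest and recovery as" muscle adapts with training. B2 says that "repeated bouts of exercise on the same day or over the course of two days elevates" immune cells and produces a larger IL-6 rise than a single bout. For iron absorption, the tracer is also tied to the period.

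At stake is the BAL minus NEG BAL comparison at a given time point. An ignored period effect inflates the standard error of the paired difference and, when the sequences are unequal in size, biases it.

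**Working it through.** **1. The plan's own figure.** B5.8.1 gives hepcidin a mean difference of 4.7 and an SD of difference of 4.9 (0.96 SD), alpha 0.05, n = 11. An exact two-sided paired t-test gives power 0.817 at n = 11, so the stated n reproduces. At n = 15 power is 0.932.

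**2. What each term estimates.** Take NEG BAL minus BAL = 4.7, SUSOPS 2 minus SUSOPS 1 = 3, and no carryover, as departures from a common mean:

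| Order | BAL | NEG BAL | Mean | NEG BAL − BAL |
|---|---|---|---|---|
| BAL first | 0 | 4.7 + 3 = 7.7 | 3.85 | 7.7 |
| NEG BAL first | 3 | 4.7 | 3.85 | 1.7 |

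The group main effect is 3.85 − 3.85 = 0. Group-by-phase is 1.7 − 7.7 = −6, which is −2 × period, with no carryover present. Adding a carryover of 2 in one order makes the group effect 1 and the interaction −8.

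**3. Where a period shift cancels.** Expected bias was obtained by generalised least squares under compound symmetry, with identical results at correlations 0.3, 0.5 and 0.7. Let π be the shift, SUSOPS 2 minus SUSOPS 1. Results at a 10/5 split:

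- *Pre and post values in both phases, constant shift:* it cancels from phase-by-time and from within-phase time contrasts.
- *Pre and post values, shift in the post value only* (the response itself changes): interaction bias is 0.33π. It stays 0.33π with a period main effect alone (post contrast 0.17π) and is 0 with period-by-time.
- *Fractional iron absorption* (one pre-value, then one post-value per phase; day 2 coded to the first phase, an assumption): bias in phase-by-time is 0.33π without period and 0 with it. Period-by-time cannot be estimated.
- *Permeability and transit:* there is no time term, so nothing cancels.

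**4. Size for the paired t-test.** Express π in SDs of the within-person difference. π and the splits are assumptions. The BAL minus NEG BAL difference has mean τ − π in BAL-first and τ + π in NEG-first. With n1 and n2 the NEG-first and BAL-first numbers:

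- Bias = π(n1 − n2)/n in absolute size: π/15 = 0.07π at 8/7, 3π/15 = 0.20π at 9/6, 5π/15 = 0.33π at 10/5.
- Variance inflation = 1 + 4π²n1n2/[n(n − 1)]. At 8/7 the multiplier is 224/210 = 1.067, so the standard error grows by √1.267 = 1.125 at π = 0.5 and √2.067 = 1.438 at π = 1.
- Period-adjusted estimate: the mean of the two sequence means, SE = ½√(1/n1 + 1/n2), n − 2 df. At 8/7 this is 0.2588, against 1/√15 = 0.2582.

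Simulated results at τ = 4.7/4.9, unadjusted alpha 0.05. The two power rows per split depend on which sequence is larger:

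| | π = 0.5 | 0.75 | 1.0 | Period-adjusted |
|---|---|---|---|---|
| 8/7, type I error | 3.1% | 1.7% | 0.8% | 5% |
| 8/7, power, bias favourable | 91% | 87% | 80% | 93% |
| 8/7, power, bias unfavourable | 87% | 78% | 64% | 93% |
| 6/5, power, bias favourable | 78% | 71% | 61% | 80% |
| 6/5, power, bias unfavourable | about 70% | 56% | 41% | 80% |

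At 10/5, type I error is 6% to 7%.

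**5. How often a real period term is deleted.** The test's noncentrality is 2π/√(1/n1 + 1/n2); at 8/7 and π = 0.5 this is 1/0.5175 = 1.93. Deletion occurs in 57%, 24% and 5% of trials at π = 0.5, 0.75 and 1.0. With three-level phase (permeability, 2 df) the figures are 65%, 32% and about 9%.

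**6. Chance of imbalance.** The documents state no ratio or blocking. Under simple randomisation of 15, 9/6 or worse has probability 0.61 and 10/5 or worse 0.30.

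**The case against.** Several points on the other side are sound.

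- **Deletion alone costs little near balance.** Applying the plan's rule to a model-based contrast at 8/7 gives type I error 4.8% to 5.1% and power 91% to 93%. It matters at 10/5: type I error about 6% to 7%, and power 85% to 88% when the bias is unfavourable, against 90%. The large losses come from the paired t-test. This stands.
- **Near balance the error is conservative.** Intervals are too wide, not too narrow. Averaged over simple randomisation, type I error is about 5% (5.0%, 4.9%, 5.2%). This stands; inflated false positives need marked imbalance.
- **The period effect may be small.** Glycogen normalisation and refeeding precede both SUSOPS, energy expenditure prescriptions are held constant, and tasks are familiarised. The repeated-bout evidence concerns bouts within two days, not periods separated by about a week. At π = 0.25 and 8/7, type I error is 4.4% and power 91% to 93%. These features reduce the likely shift but do not rule it out.
- **Carryover can also enter group-by-phase**, and with three-level phase the term contains a second contrast, average SUSOPS versus baseline by group. This qualifies the label but does not supply a protected period term.
- **The power figures use hepcidin as a yardstick.** Primary and appetite post hoc tests follow a significant interaction and carry a Bonferroni correction, which the simulation leaves out. The documents give no effect size for iron absorption. The figures show scale and do not predict power for each outcome.

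**Conclusion.** The concern holds and should be fixed. The group-by-phase term is the period contrast, it is kept only if significant, and the paired t-tests never use it. Near balance the cost is lost power and over-wide intervals. At 10/5 it is bias of a third of the period shift, with type I error of 6% to 7%. Among primary-objective outcomes, fractional iron absorption is the most exposed, because even a constant shift enters its diet comparison. Permeability and transit are exposed in the same way. IL-6 and hepcidin are protected in the phase-by-time test against a constant shift, but not against a change in the size of the response, nor in post hoc diet comparisons at a single time point.

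The identification of the term rests on the design alone. The sizes rest on assumed period shifts and sequence splits; they are small at 0.25 SD and material from about 0.5 SD. The DESeq2 models and the omics t-tests are outside this point.

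**What to change.** In the four model sets, replace the removal rule with wording to this effect:

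> Period (SUSOPS 2 = 1; SUSOPS 1 and baseline = 0) is a fixed effect. Period-by-time is added wherever two or more time points are measured in both SUSOPS phases. Neither is removed on significance. Group (sequence) is reported descriptively and is not used to select the model. BAL minus NEG BAL post hoc comparisons are Bonferroni-adjusted contrasts from the fitted mixed model.

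For fractional iron absorption, permeability and transit, include period only. For iron absorption, also state how the single day 2 value is coded in the phase and time factors.

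This changes SAP wording only. Period uses one degree of freedom, and period-by-time one more per additional time point. If there is no period effect, power at 0.96 SD with the period term goes from 93.2% to 92.8% at 8/7, from 93.2% to 89.9% at 10/5, and from about 82% to 80.5% at 6/5. The power cost of period-by-time over the full sampling schedule was not calculated.
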